10.4.2. Eliciting Adverse Events

The investigator or designee will ask about AEs by asking the following standard questions:

- How are you feeling?
- Have you had any medical problems since your last visit?
- Have you taken any new medicines since your last visit?

10.5. Specific Instructions for Recording Adverse Events and Serious Adverse Events

10.5.1. Diagnosis versus Signs and Symptoms

If a diagnosis is known at the time of reporting, this should be recorded in the eCRF (and SAE report, as applicable), rather than the individual signs and symptoms (e.g., record only hepatitis rather than elevated transaminases, bilirubin, or jaundice). However, if a constellation of signs and/or symptoms cannot be medically characterized as a single diagnosis or syndrome at the time of reporting, each individual AE should be recorded as an SAE or AE on the eCRF (and SAE report, if applicable). If a diagnosis is subsequently established, it should replace the individual

signs and/or symptoms as the AE term on the eCRF (and SAE report, if applicable), unless the signs/symptoms are clinically significant.

10.5.2. Adverse Events Occurring Secondary to Other Events

In general, AEs occurring secondary to other AEs (e.g., clinical sequelae or a cascade of AEs) should be identified by their primary cause. For example, if severe vomiting is known to result in dehydration, it is sufficient to record only vomiting as the SAE or AE on the eCRF (and SAE report, if applicable). However, if a patient initially has a non-serious AE, and it subsequently becomes an SAE, both AEs should be reported separately on the eCRF. The onset date of the non-serious AE should be recorded as the start date of the non-serious AE. The onset date of the SAE should be recorded as the start date when the non-serious AE becomes an SAE.

10.5.3. Persistent or Recurring Adverse Events

A persistent AE is one that extends continuously, without resolution, between patient evaluation timepoints. Such AEs should only be recorded once on the AE eCRF (and SAE report, if applicable). If a persistent AE worsens in grade, it should be recorded as a new AE on the eCRF (and a stop date should be recorded in the previous AE).

A recurrent AE is one that occurs and resolves between patient evaluation timepoints, and subsequently recurs. All recurrent AEs should be recorded separately on the eCRF (and SAE report, if applicable).

10.5.4. Disease Progression

Disease progression is measured as an efficacy endpoint and is not considered to be an AE. However, if there are separate identifiable clinical sequelae that result from disease progression, those sequelae are reportable as AEs. For instance, a patient with pleural effusion presents with shortness of breath. The cause of the shortness of breath is a pleural effusion resulting from disease progression. The AE term should be reported as “pleural effusion” instead of disease progression or metastasis to lungs. If a patient has a seizure that is determined to be associated with a brain metastasis, the term “seizure” should be recorded as the AE instead of disease progression or brain metastasis. If a patient experienced multi-organ failure due to disease progression, the term “multi-organ failure” should be reported as the AE instead of disease progression. Deaths that are assessed by the investigator as solely due to disease progression should be recorded on Study Completion or Early Discontinuation eCRF as efficacy data. They should not be reported as an SAE. If deaths are assessed by the investigator as not solely due to disease progression, whether they are assessed as related or not related to the study drug, they should be reported as SAE immediately.

If there is any uncertainty regarding whether an AE is due to disease progression, it should be reported as an AE.

10.5.5. Death

Death is an outcome, not an event. If an AE/SAE results in death, then the term of the AE that caused or contributed to fatal outcome should be recorded as the single medical concept. If the cause of death is unknown and cannot be ascertained at the time of reporting, record “unexplained death”.

10.6. Prompt Reporting of Serious Adverse Events

10.6.1. Timeframes for Submitting Serious Adverse Events

Serious adverse events will be reported promptly (within 24 hours) to the sponsor or designee as described in Table 4 and the Study Manual once the investigator determines that the AE meets the protocol definition of an SAE.

Table 4: Time Frame for Reporting Serious Adverse Events to the Sponsor or Designee

Type of SAE	Initial SAE Report	Documentation	Timeframe for sending follow-up report	Documentation method	Reporting method
All SAEs	Within 24 hours of first knowledge of the SAE	SAE report	As expeditiously as possible	SAE report	Email or fax SAE report form

SAE, serious adverse event.

10.6.2. Completion and Transmission of the Serious Adverse Event Report

Once an investigator becomes aware that an SAE has occurred in a patient, he/she will report the information to the sponsor within 24 hours as outlined in Section 10.5.1. The SAE Report will always be completed as thoroughly as possible with all available details of the event and forwarded to the sponsor or designee within the designated timeframes.

If the investigator does not have all information regarding an SAE, he/she is not to wait to receive additional information before notifying the sponsor or designee of the SAE and completing the form. The form will be updated when additional information is received. The investigator will always provide an assessment of causality at the time of the initial report as described in Section 10.1.1.2. The sponsor will provide contact information for SAE receipt.

10.6.3. Regulatory Reporting Requirements for Serious Adverse Events

The investigator will promptly report all SAEs to the sponsor in accordance with the procedures detailed in Section 10.5.2. The sponsor has a legal responsibility to notify, as appropriate, both the local regulatory authority and other regulatory agencies about the safety of a product under clinical investigation. The investigator, or responsible person according to local requirements, will comply with the applicable local regulatory requirements related to the reporting of SAEs to regulatory authorities and the IRB/IEC.

All suspected unexpected serious adverse reactions will be submitted to all applicable regulatory authorities and investigators for pamiparib studies.

When a study center receives an initial or follow-up safety report or other safety information (e.g., revised Investigator’s Brochure) from the sponsor, the investigator or designated responsible person is required to promptly notify his/her IRB or IEC. The investigator should place copies of Safety Reports from the sponsor in the Investigator Site File.

10.7. Pregnancy Reporting

If a female patient or the partner of a male patient becomes pregnant while receiving investigational therapy or within 6 months after the completion of the last dose of study drug, a pregnancy report form should be completed and expeditiously submitted to the sponsor to facilitate outcome follow-up. Information on the status of the mother and child will be forwarded to the sponsor. Generally, follow-up will be no longer than 6 to 8 weeks following the estimated delivery date. Any premature termination of the pregnancy will be reported.

While pregnancy itself is not considered to be an AE or SAE, any pregnancy complication or elective termination of a pregnancy for medical reasons will be recorded as an AE or SAE.

An abortion, whether accidental, therapeutic, or spontaneous should always be reported as an SAE. Similarly, any congenital anomaly/birth defect in a child born to a patient exposed to the study drug should be recorded and reported as an SAE.

10.8. Expedited Reporting to Health Authorities, Ethics Committees, and Investigators

The sponsor will promptly assess all SAEs against cumulative study drug experience to identify and expeditiously communicate new safety findings to regulatory authorities, investigators, IRBs and IECs based on applicable legislation.

To determine the reporting requirements for individual SAEs, the sponsor will assess the expectedness of the SAEs using the following reference documents:

- Pamiparib (BGB-290) Investigator's Brochure [59]

11. STATISTICAL CONSIDERATIONS AND ANALYTICAL PLAN

All statistical analyses will be performed by the sponsor or designee after the study is completed and the database is locked and released. Details of the statistical analyses will be included in a separate statistical analysis plan (SAP).

11.1. Primary, Secondary, and Exploratory Study Endpoints

Please refer to Section 3 for a full listing of study endpoints.

11.2. Statistical Analysis

For the dose escalation phase, data will be summarized by dose level. For the dose expansion phase, data will be summarized by cohort.

Descriptive statistics will be mainly used in describing the anticancer activities and tolerability of the pamiparib and TMZ combination regimens. Confidence intervals will be constructed to describe the precision of the point estimates of interest (e.g. objective response rate and disease control rate).

11.2.1. Analysis Populations

Safety Population includes all patients who received any dose of pamiparib and/or TMZ. The Safety Population will be used for all safety analyses.

Efficacy Evaluable Population includes patients in the Safety Population who had measurable disease (or evaluable disease for patients enrolled into the dose escalation phase) at baseline (or prostate cancer patients as per inclusion criterion 14f) and had at least one post-baseline tumor assessment unless discontinued treatment due to clinical progression or death prior to tumor assessment.

DLT Evaluable Population includes patients who received $\geq 70\%$ of each study drug during the DLT assessment window and had sufficient safety evaluation. Additionally, patients who had a DLT event during the DLT assessment window despite receiving $< 70\%$ of the scheduled dose will also be considered evaluable.

PK Population includes all patients for whom valid pamiparib PK parameters can be estimated.

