8.4. End-of-Treatment Visit

Patients who discontinue from study drug for any of the reasons listed below will undergo an EOT visit within 7 days of discontinuation of all study drugs. If routine laboratory tests (e.g., hematology, clinical chemistry) were completed ≤ 7 days before the EOT Visit, these tests do not need to be repeated.

However, the EOT visit may occur later than 7 days after discussion with the Medical Monitor for specific circumstances, such as prolonged hospitalization. If the EOT Visit did not occur until 30 days (± 7 days) or later after the last dose of pamiparib and TMZ, the EOT Visit may also be used as the Safety Follow-up Visit.

Patients with a required EOT visit may discontinue study drug for any of the following reasons:

- Disease progression

- Investigator decision
- Adverse event(s)
- Pregnancy
- Patient withdrew consent for study drug
 - Patients may voluntarily withdraw consent from study drug at any time
 - Patients may continue to participate in the Follow-up Phase, if the patient withdraws consent from the Treatment Phase
- Start of other anticancer therapy
- Patient noncompliance
 - Study site staff should first counsel patients who are significantly noncompliant (e.g., missing 2 treatment cycles) on the importance of study drug compliance and drug accountability. The investigator may, in consultation with the medical monitor, discontinue patients from treatment who are consistently noncompliant

The reason for discontinuation from study drug will be recorded on the eCRF.

All the assessments performed for the EOT visit are listed in the Schedule of Assessments ([Appendix 1 Table 1](#)).

The visit at which the assessment showed progressive disease may be used as the EOT visit provided that all required assessments were performed. A CT does not have to be repeated at the EOT visit if it was performed within 14 days of the visit or at a prior response evaluation that documented progressive disease. ECG does not have to be repeated if it was performed within 14 days of the EOT visit.

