11.2.5. Efficacy Analyses

No formal hypothesis testing is planned in this Phase 1b study.

For solid tumors other than prostate cancer, tumor assessment based on investigator assessment according to RECIST v1.1 will be used to calculate ORR, DCR, PFS, and DOR, as well as timepoint estimate PFS-6m. Overall survival (OS) and OS-6m will be summarized as well. For patients with ovarian cancer, tumor response may also be assessed by investigators based on GCIG criteria which use carcinoma antigen-125 (CA-125) in combination with RECIST v1.1 ([Appendix 9](#)).

For patients with prostate cancer, PSA and tumor lesions will be evaluated together to determine the tumor response according to PCWG2 criteria ([Appendix 10](#)).

ORR is defined as the proportion of patients who have a best overall response (BOR) of CR or PR, where BOR is defined as the best response recorded from the first dose of study drugs until data cut, disease progression, or start of new anti-neoplastic treatment. Binomial exact 90% and 95% confidence intervals will be calculated for ORR in each cohort.

DCR is defined as the proportion of patients with BOR of CR, PR, and SD. It will be summarized similarly as ORR.

PFS is defined as the time from the date of the first dose of study drugs to disease progression or death, whichever occurs first.

PFS censoring rule will follow FDA *Guidance for Industry, Clinical Trial Endpoints for Approval of Cancer drugs and Biologics* (2007). Patients who have a clinical determination of progression should undergo imaging and laboratory assessments, if possible, to correlate radiographic findings with the clinical findings. Data for patients without disease progression or death by the time of analysis will be censored at the time of the last tumor assessment. Data from patients who are lost to follow-up prior to documented disease progression will be censored at the last tumor assessment date when the patient is known to be progression-free. More details will be given in the SAP.

DOR is defined as the time from the date of the earliest documented response to disease progression or death for any cause, whichever occurs earlier. Only responders will be included in the DOR calculation.

OS is defined as the time from the date of the first dose of study drugs to death.

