6.1 ANALYSIS POPULATIONS

- Safety Analysis Set (SAF): includes all patients enrolled into the study who receive any dose of pamiparib and/or TMZ. The Safety Analysis Set will be used for overall survival analysis and safety analyses.
- Efficacy-Evaluable Analysis Set: includes patients in the SAF who had evaluable disease in the dose escalation phase (or measurable disease in the dose expansion phase) at baseline and had at least one postbaseline tumor assessment unless discontinued treatment due to clinical progression or death prior to tumor assessment.

Evaluable disease means patients may have measurable (target lesions) or non-measurable lesions (non-target lesions); measurable disease means patients must have at least 1 measurable lesion (target lesions) and may or may not have non measurable lesions (non-target lesions).

- DLT Evaluable Analysis Set: includes patients who received $\geq 70\%$ of BGB-290 and TMZ during the DLT assessment window (Cycle 1). Additionally, patients who had a DLT event during the DLT assessment window despite receiving $< 70\%$ of the scheduled dose will also be included.
- PK Analysis Set: includes patients who received any dose of BGB-290 or TMZ, and contributed at least one plasma concentration.

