6.3.2 Secondary Efficacy Endpoints

- Pharmacokinetic parameters of BGB-290 and TMZ, including but not limited to C_{trough}
Refer to Section 6.3.6 for more detail.
- Disease Control Rate (DCR) by investigator

DCR is defined as the proportion of subjects with BOR of CR, PR, or stable disease (SD). Similar to ORR, two-sided binomial exact 90% confidence intervals will be calculated for DCR in each cohort. The table for DCR will be summarized in both SAF and Efficacy Evaluable Analysis Set. Patients without evaluable postbaseline tumor assessment will be considered as non-responders in the safety analysis set.

- Duration of Response (DOR) by investigator

DOR is defined as the time (month) from the date of the earliest documented CR or PR (that is subsequently confirmed) to disease progression or death due to any cause, whichever occurs earlier. The tables for confirmed and nonconfirmed DOR will be summarized in efficacy evaluable set and only responders will be included in the DOR calculation.

Kaplan-Meier method will be used to estimate DOR, and corresponding quartiles (including the median) in the responders. A two-sided 90% CIs of median will be calculated for each cohorts using generalized Brookmeyer and Crowley method (Brookmeyer & Crowley, 1982).

Censoring rule for DOR will follow PFS censoring rule mentioned in FDA Guidance for Industry Clinical Trial Endpoints for the Approval of Cancer Drugs and Biologics (2018). The censoring rules are described in Appendix 10.2.

- PFS and PFS-6m by investigator

PFS is defined as the time (months) from the date of the first dose of combination treatment to disease progression or death due to any cause, whichever occurs first. The PFS-6m is defined as the percentages of subjects who remain alive and progression-free at 6 months. PFS censoring rules are described in Appendix 10.2. If a patient meets the criteria for more than 1 censoring rule, PFS will be censored at the earliest censoring date. The tables for PFS and PFS-6m will be summarized in Efficacy Evaluable Analysis Set.

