8 CHANGES IN THE PLANNED ANALYSIS

There are some changes in the planned analysis and they are listed below:

- DLT will be provided in a listing and no descriptive statistics will be provided.
- Subgroup analysis for ORR will only be done for SCLC patients in chemosensitivity and number of prior regimens.
- All by-visit analyses will be removed, and the following will be performed: hematology data will be presented in a shift table and serum chemistry will be provided in a listing. ECG will be listed. A listing of QTcF will be provided for patients with abnormal postbaseline values and abnormal changes from baseline. ECOG and vital signs will be provided in listings.
- Ninety percent CIs will be presented instead of 95% CIs.
- OS analyses will be conducted in SAF instead of Efficacy Evaluable Analysis Set. Only PFS and OS analyses will be conducted and not PFS-6m and OS-6m analyses.
- Efficacy analyses such as ORR, PFS and DOR will be based on radiographic responses or radiographic progression.
- Treatment-emergent SAEs, treatment-related TEAEs, TEAEs with grade 3 or above, and treatment-related SAEs will be summarized by SOC, PT and CTCAE grade. AEs that led

to death and AEs that led to treatment discontinuation, dose reduction or dose interruption will only be listed.

- Number of treatment cycles will not be summarized. Instead, reasons for dose reduction, dose interruption and missed dose will be summarized.

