10.2 CENSORING RULES

Table 3 shows the primary censoring rules for the derivation of PFS.

Table 3 Censoring Rules for Analysis of PFS

No.	Situation	Date of Progression or Censoring	Outcome
1	No baseline tumor assessments or no post baseline tumor assessment	Reference start date (e.g., C1D1)	Censored
2	Progression documented on scheduled visit or between scheduled visits	Date of first radiologic PD assessment	Progressed
3	No progression at the time of data cutoff or withdrawal from study	Date of last adequate radiologic assessment prior to or on date of data cutoff or withdrawal from study	Censored
4	Treatment discontinuation for undocumented progression	Date of last radiological assessment of measured lesions	Censored
5	New anticancer treatment started	Date of last radiological assessment of measured lesions prior to or on date of new anticancer treatment	Censored
6	Death before first PD assessment	Date of death	Progressed
7	Death between adequate assessment visits*	Date of death	Progressed
8	Death or PD after two or more consecutive missed visit**	Date of last adequate radiologic assessment before missed tumor assessments	Censored

9	A patient meets the criteria for more than 1 censoring rules above	Date of the earliest censoring date among all events	Censored
---	--	--	----------

Abbreviations: CR=complete response, PD=progressive disease, PR=partial response, SD=stable disease.

*Adequate tumor assessment is a radiologic assessment of CR, PR, SD, non-CR/non-PD or PD as determined by investigators or by IRC.

**More than one missed visit is defined if the duration between the last tumor assessment and death or PD is longer than 2 scheduled visits, which is 17 weeks (119 days).

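### PFS is tabulated only in the Efficacy Evaluable set, which on its natural reading leaves out a patient who stops drug for toxicity and dies before any scan, although OS counts that death

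*Protocol*

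**What the plan says.** **Set for PFS.** SAP 6.3.2: "The tables for PFS and PFS-6m will be summarized in Efficacy Evaluable Analysis Set". No version in the Safety Analysis Set (SAF) is planned, although the same section gives disease control rate in both sets. Protocol 11.2.5 names no set for PFS, so the choice is the SAP's.

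**Who is in the set.** Besides a baseline disease requirement, Protocol 11.2.1 admits a treated patient who "had at least one post-baseline tumor assessment unless discontinued treatment due to clinical progression or death prior to tumor assessment". SAP 6.1 has the same condition: "had at least one postbaseline tumor assessment unless discontinued treatment due to clinical progression or death prior to tumor assessment".

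**Reasons for stopping.** Protocol 8.4 lists adverse events, investigator decision and withdrawal of consent for study drug as reasons distinct from disease progression.

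**What counts as a PFS event.** Protocol 11.2.5: "PFS is defined as the time from the date of the first dose of study drugs to disease progression or death, whichever occurs first". SAP 6.3.2 ends PFS at "disease progression or death due to any cause, whichever occurs first".

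**SAP Table 3 (Section 10.2).** Row 6, "Death before first PD assessment", is an event at the date of death. Row 1 censors a patient with no post-baseline tumor assessment at the reference start date, for example Cycle 1 Day 1. Row 9 settles conflicts between censoring rules only.

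**Set for OS.** SAP Section 8: "OS analyses will be conducted in SAF instead of Efficacy Evaluable Analysis Set". SAP 6.1 agrees.

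**The concern.** The endpoint definition and row 6 say that an early death is a PFS event. The analysis set can remove the patient before row 6 is reached. Whether an unscanned patient stays depends on the recorded reason for stopping drug, which is known only after treatment has begun. A death during treatment, or after stopping for clinical progression, is kept. A death after stopping for toxicity is not.

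Losing such patients is unlikely to be random. Appendix 1 of the Protocol schedules imaging at the end-of-treatment visit, and Sections 7.7 and 8.5.2 continue it every 8 weeks after drug is stopped without progression. Someone who stops for toxicity and still has no scan has probably become too ill or died. That is inference, not something the documents state.

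At stake are an upward shift of each cohort's PFS estimate and a mismatch in which one death counts in OS and is absent from PFS.

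**Working it through.** **Figures in the plan.** The documents give no PFS assumption, event count or rate of such deaths, so there is no plan figure to reproduce. The sizing tables (Protocol Table 5, SAP Table 1) concern ORR and do not bear on this point.

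**Inputs**
- Cohort size n: 20 to 25 (Protocol 11.4, SAP Section 5).
- First scheduled scan: 8 weeks ± 7 days (Protocol 7.7), so at latest day 56 + 7 = 63, about week 9.
- k, the number of patients per cohort who stop for a reason outside the exception and die unscanned: assumed 0 to 3.
- Median PFS of the other n−k patients: assumed 3, 4 or 6 months, exponential.

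**Step 1, membership.** Take a patient who stops for an adverse event in Cycle 1, has no end-of-treatment scan and dies in week 7. There is no post-baseline scan, and treatment was not stopped for clinical progression or death. The patient is outside the Efficacy Evaluable set and inside the SAF: no PFS record, one OS event.

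**Step 2, effect on the curve.** With no other early censoring, let x patients be event-free at a time t after these deaths. The Efficacy Evaluable estimate is x/(n−k). The estimate in all treated patients, with the deaths as events, is x/n. The ratio is n/(n−k):

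| n | k=0 | k=1 | k=2 | k=3 |
|---|---|---|---|---|
| 20 | 1.00 | 20/19 = 1.05 | 20/18 = 1.11 | 20/17 = 1.18 |
| 25 | 1.00 | 25/24 = 1.04 | 25/23 = 1.09 | 25/22 = 1.14 |

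**Step 3, worked cohorts.** The other patients' event times are placed at exponential quantiles, −(m/ln 2)·ln(1−(i−0.5)/(n−k)) for assumed median m and i = 1 to n−k. The early deaths fall at 1.2 to 1.4 months.

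| n, k, assumed median | 6-month PFS, Efficacy Evaluable | 6-month PFS, all treated | Median, Efficacy Evaluable | Median, all treated |
|---|---|---|---|---|
| 25, 1, 4 mo | 8/24 = 33.3% | 8/25 = 32.0% | 3.8 mo | 3.8 mo |
| 20, 2, 4 mo | 6/18 = 33.3% | 6/20 = 30.0% | 3.7 mo | 3.1 mo |
| 25, 3, 4 mo | 8/22 = 36.4% | 8/25 = 32.0% | 3.7 mo | 3.3 mo |
| 20, 3, 6 mo | 8/17 = 47.1% | 8/20 = 40.0% | 6.0 mo | 4.2 mo |

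Over all combinations with k of 1 to 3, the 6-month gap runs from 1.0 point (6/24 = 25.0% against 6/25 = 24.0%) to 7.1 points (47.1% against 40.0%). The 6-month rate is only an illustration: SAP Section 8 drops the PFS-6m analysis while 6.3.2 keeps it, but the ratio applies to any later time point.

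**Step 4, does changing the set suffice?** In the SAF our patient fits row 1 (censored at Cycle 1 Day 1) and row 6 (event at death). Row 9 does not rank a censoring row against an event row. When row 1 was applied to the k patients, the SAF curve equalled the Efficacy Evaluable curve in every case, because a patient censored on day 1 leaves the risk set before any event. The set and row 1 must change together.

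**The case against.** **The exception can be read more loosely.** The final timing words can be attached to death alone, giving two separate exceptions: stopping for clinical progression, or dying before a tumor assessment. Every pre-scan death would then stay in the set, and row 6 is consistent with that intention. The grammar favours tying both to the reason for stopping, but the sponsor may have meant the looser sense. This stands as a reason to make the text explicit, not as a reason to leave it.

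**The group is narrow.** A patient is lost only after stopping for a reason outside the exception, missing the end-of-treatment scan (that visit is due within 7 days of stopping) and dying before the first 8-week scan, or later if that scan is missed. A patient who withdraws from the study altogether contributes no further data (Protocol 8.6), so only withdrawal from study drug is relevant. In a given cohort k may well be 0. This stands.

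**The shift is small beside the noise.** In simulated cohorts of 25 with an assumed 4-month median, the mean sample median was about 4.1, 3.9, 3.6 and 3.4 months with 0, 1, 2 and 3 such deaths counted. The standard deviation of one cohort's median was about 1.2 months. PFS is secondary, nothing is formally tested, and OS already shows these deaths. All of this limits the importance of the point, but the error runs in one direction and is avoidable.

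**Stronger readings to avoid.** A reader might infer that the set removes only early failures. It does not: it also drops living patients without a scan and, in expansion, patients without measurable disease. A reader might also infer that all early deaths vanish from PFS, but deaths on treatment and deaths after clinical progression are kept.

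**Conclusion.** The concern holds as a modest, correctable inconsistency in a secondary analysis. On the natural reading of the exception, PFS in the Efficacy Evaluable set omits deaths that its own definition and row 6 call events, while OS in the SAF includes them. For k such deaths among n treated, the later PFS curve is overstated by n/(n−k): 4% to 18% relative for an assumed k of 1 to 3 and n of 20 to 25, and nothing at k = 0. The median may or may not move; it did not at n = 25, k = 1.

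This rests on that reading, on no other early censoring, and on an assumed k. The documents therefore do not support a claim that PFS in this trial will be materially biased. Nor can the point be separated from the conflict between rows 1 and 6, since that conflict decides whether a change of set does anything.

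**What to change.** 1. In SAP 6.3.2 and Section 8, analyse PFS and its event-free rates in the SAF, as for OS. Keep the Efficacy Evaluable version as supportive.
2. In SAP Table 3, limit row 1 to patients who did not die before a first post-baseline assessment, so that row 6 takes precedence and the death is an event on its date. Row 8 still applies: a death more than 119 days after the last tumor assessment remains censored.
3. If the Efficacy Evaluable set is kept for PFS, extend its exception to death from any cause before the first tumor assessment, whatever the reason for stopping treatment, and make the same change to row 1.

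The cost is SAP wording and a rerun of the same program on another set; no new data are needed. Living patients without a scan remain censored at Cycle 1 Day 1 and do not alter the curve. The SAF also brings in patients without measurable disease at baseline; the footnote to Table 3 already accepts non-CR/non-PD as an adequate assessment. The downside is that PFS may become slightly less favourable.
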